### **13.3 Quality Assurance (Auditing)**

According to the ICH-GCP (R2) guidelines, audits will be performed according to a quality assurance system. These may be conducted by the coordinating investigator.

During an audit, the planning, conduct and analysis of a study might be checked for compliance with the national laws and the requirements of the ICH-GCP (R2) guideline and will be stated by the conducting authority.

This might include checking the data management and organisation at the study site and inspecting institutions and source documents. The aim of quality assurance is to ensure that the results and conclusions described in the final report can be correctly deduced from the raw data.

All persons performing an audit undertake in writing to treat all patient-relevant data confidentially restrict the use of such data to the purposes agreed by the patient in writing.

Proposed audit dates, characteristics of the selected patients and further information will be transmitted to the investigator by the CRA in a timely manner.

## 14 Biostatistical Planning and Analysis

Before the start of the final analysis a detailed statistical analysis plan (SAP) will be prepared. This will be completed during the 'blind review' of the data, at the latest. This blind review, i.e. a checking and assessment of the data, will be performed after the end of the recruitment period and the planned follow-up period without looking at the randomised treatment for each patient. If the SAP contains any changes to the analyses outlined in the trial protocol, they will be marked as such, and reasons for amendments will be given.

All statistical programming for analysis will be performed with the Statistical Analysis System (SAS).

### 14.1 Study Design

Multi-centre, randomised controlled, open-label trial, stratified randomised by study site, with two active groups and one control parallel group.

### 14.2 Objectives and Endpoints

See Section 2.

### 14.3 Sample Size Calculation

Sample size calculation is based on assumptions on the proportion of patients with at least one fall during a 6-months period. The proportion of patients with at least one fall is assumed as 50% in the standard care group [50, 59]. A decrease of this proportion to 35% is considered as clinically relevant and as achievable by EYT as well as by Tai Chi [63]. The study is planned with 80% power to show a difference between treatments at two-sided level alpha of 5%, when proportions of fallers are 50% with standard care and 35% both with EYT and with Tai Chi. Based on the chi-square distribution, this requires 155 patients per group (calculated with NQuery Advisor 7.0). The sample size calculation was performed for the three-group comparison. To account for multiplicity issues in this three-group comparison, a closed test procedure at two-sided level alpha of 5% will be used, i.e. the global null hypothesis of no differences between any of the three intervention types will be tested first, and if it can be rejected, pairwise group comparisons will be conducted each at two-sided level alpha of 5%. The two-group comparison of EYT versus standard care has a power of 80%, when the proportion of fallers is reduced from 50% to 34.3%. The two-group comparison of EYT versus Tai Chi has a power of 80%, when the difference in the proportion of fallers is 15%. To account for a certain amount of non-compliance and incomplete observations, 550 patients will be randomised in a ratio of 1:1:1.

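### The 80% powers quoted for the pairwise comparisons are stand-alone chi-square figures. Within the closed procedure, EYT versus standard care has about 75% at 50% vs 34.3% and 71% at the planned 35%, and the 15-point EYT–Tai Chi figure lacks a base rate.

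*Protocol*

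**What the plan says.** All the figures are in Protocol section 14.3. The main sizing statement is "The study is planned with 80% power to show a difference between treatments at two-sided level alpha of 5" per cent. It assumes that half of the standard care arm and 35% of each active arm will fall. The result is given as "Based on the chi-square distribution, this requires 155 patients per group (calculated with NQuery Advisor 7.0"), and the section adds that "The sample size calculation was performed for the three-group comparison".

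The multiplicity rule follows. A global test of equality across the three arms comes before anything else; "if it can be rejected, pairwise group comparisons will be conducted each at two-sided level alpha of 5" per cent. Section 14.5.1 repeats this rule for the primary Cox analysis.

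Two pairwise statements come directly after the rule. For EYT against control: "The two-group comparison of EYT versus standard care has a power of 80%, when the proportion of fallers is reduced from 50% to 34.3" per cent. For the two active arms: "The two-group comparison of EYT versus Tai Chi has a power of 80%, when the difference in the proportion of fallers is 15" per cent. The section does not say whether either figure allows for the preceding global test, and the second names no proportion from which the 15 points are measured. The randomised total is then raised to 550 to cover non-compliance and incomplete observation, without a stated rate.

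**The concern.** Under the closed procedure a pairwise comparison can succeed only if the global test also rejects. Its power is therefore the probability that both tests are significant, which cannot exceed the power of the pairwise test alone. The pairwise figures come right after the rule, so a reader would naturally take them as powers under that rule.

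This matters because section 2.1 frames the primary question as whether EYT (and Tai Chi) can reduce the risk of falling. The 80% on which the trial is sized is the chance of finding some difference among three arms. The chance of showing that EYT beats standard care is lower, and section 14.3 never gives it at the planning value of 35%. For EYT versus Tai Chi, a difference in proportions does not fix the power unless one of the proportions is given too.

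**Working it through.** **Inputs (section 14.3).** Two-sided α = 0.05; 155 per arm; planned proportions 50/35/35; chi-square basis; global test first, then pairwise tests at 5%; 550 randomised 1:1:1, about 183 per arm.

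**Step 1: the global test reproduces.** Non-centrality λ = n Σ(pᵢ − p̄)² / [p̄(1 − p̄)]. With p̄ = 0.40, Σ(pᵢ − p̄)² = 0.0100 + 0.0025 + 0.0025 = 0.0150, so λ = 155 × 0.0150/0.24 = 9.69. On 2 df (critical value 5.99) the power is 80.2%. With n = 154 it is 79.96%, so 155 is right.

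**Step 2: the pairwise 80% reproduces as a stand-alone power.** Power = Φ{[d√n − 1.96√(2p̄q̄)] / √(p₁q₁ + p₂q₂)}, where p̄ is now the mean of the two proportions and q = 1 − p.

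- 50% vs 34.3%: [0.157 × 12.450 − 1.96 × 0.6983]/0.6895 = 0.850, power 80.2%.
- 50% vs 35%: [0.150 × 12.450 − 1.96 × 0.6991]/0.6910 = 0.720, power 76.4%.

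**Step 3: power within the closed procedure.** This is P(global p < 0.05 and pairwise p < 0.05), simulated with 400,000 binomial trials per scenario and Pearson chi-square tests. EYT versus standard care at 50% vs 34.3%, 155 per arm:

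| Tai Chi | Stand-alone | Closed procedure |
|---|---|---|
| 25% | 80% | just under 80% |
| 30% | 80% | 79% |
| 34.3% | 80% | 76% |
| 35% | 80% | 75% |
| 42.5% | 80% | 70% |
| 50% | 80% | 76% |

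The loss is largest when Tai Chi lies midway. The third arm then adds almost nothing to the global statistic, which must pass 5.99 on 2 df where the pairwise statistic needs only 3.84 on 1 df. If Tai Chi is clearly better than EYT, the global test almost always rejects and nothing is lost.

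At the planned 50/35/35:

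| Patients per arm | Global | EYT vs standard care, stand-alone | EYT vs standard care, closed | Both active arms vs standard care, closed |
|---|---|---|---|---|
| 155 | 80% | 76% | 71% | 63% |
| 183, complete data | 87% | 83% | 80% | 73% |

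**Step 4: EYT versus Tai Chi, 15 points, 155 per arm.** Standard care is taken as 50% for the closed-procedure column.

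| Pair | Stand-alone | Closed procedure |
|---|---|---|
| 35% vs 20% | 84% | 85% (same simulation without the global test: 85%) |
| 41% vs 26% | 80% | 80% |
| 50% vs 35% | 76% | 71% |

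For 35% vs 20% the stand-alone formula gives 84.4% and the simulation about 84.7%. The global test rejects in more than 99.9% of those trials, so it costs nothing.

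**The case against.** Four points can fairly be made for the protocol.

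- **The figures are correctly computed.** Section 14.3 speaks of a two-group comparison, and 80% is right for one. A reader might infer an arithmetic error; there is none. The section also says that the sizing was for the three-group comparison. Quoting 34.3% rather than 35% already implies that the stand-alone power at 35% is below 80%. This stands, but nothing tells the reader that the pairwise figures leave out the rule stated just before them.
- **The 15-point statement is not simply false at 35%.** A reader might infer that it fails once one arm is at the planned 35%. If the other arm is 15 points better, the power is about 84–85% and the protocol is conservative. It falls short only if the other arm is at 50%, no better than the assumed standard care, which departs from the plan that both active arms reach 35%. What stands is the missing base rate.
- **The trial will use Cox regression, not chi-square.** Section 14.5.1 expects a gain in power but gives no amount. A check with unadjusted log-rank tests, assuming exponential times to first fall and complete six-month follow-up, gives roughly 77–78% within the closed procedure at 50/34.3/35 and 73–74% at 50/35/35 with 155 per arm. That narrows the gap without closing it. Adjustment for BBS and age is not included.
- **The enlarged sample would restore 80%.** With 183 complete patients per arm, the closed-procedure chi-square power at 50/34.3/35 is about 83%. But the protocol reserves the excess over 3 × 155 = 465 (85 of 550, or 15.5%) for non-compliance and incomplete observation, so it cannot also support the 80%.

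**Conclusion.** The point holds as one of labelling and missing specification. On the protocol's own chi-square basis with 155 per arm, the stated 80% for EYT versus standard care is about 75–76% within the closed procedure when Tai Chi is at 34.3–35% or 50%. It drops to about 70% at 42.5% and loses almost nothing at 25%. At the planned 50/35/35 the power is about 71% for EYT and about 63% for both active arms. The 63% contradicts no printed figure, because the protocol claims no power for winning both comparisons. The 80% for EYT versus Tai Chi cannot be interpreted without a base rate: it is exact only near 26% vs 41%.

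A reader might go further and infer that the type I error is inflated or that 550 patients are too few. Neither follows. For three groups the closed procedure controls the error rate, and the global-test sizing is correct. The results assume binary outcomes, equal arms and the proportions shown; the planned Cox analysis may do somewhat better. This is worth correcting, because it overstates the power of the comparison that readers care about most and costs almost nothing to put right.

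**What to change.** Keep 550 patients, the closed procedure, the levels and all tests. Reword section 14.3 to:

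1. state that 80% at 155 per arm is the power of the global three-group test at 50/35/35;
2. either label the pairwise figures as stand-alone chi-square powers, or replace them with the closed-procedure values at 50/35/35: about 71% for EYT versus standard care and 63% for both active arms at 155 per arm, and about 80% and 73% at 183 per arm with complete data;
3. give the base rate for the 15-point EYT–Tai Chi difference, for example by quoting the power at 35% vs 20% and at 35% vs 50%;
4. note that these are binary chi-square figures and that the Cox analysis may have somewhat more power.

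The cost is a few sentences and a slightly less favourable statement of power. No patients are added, and neither conduct nor error control changes.

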### 14.4 Definition of Populations Included In the Analyses

The trial will be analysed according to the 'intention-to-treat principle'. That is, the primary analysis for comparison of the treatment groups will be based on the 'full analysis set' (FAS).

The FAS includes all randomised patients, and patients are analysed as belonging to their randomised arm, regardless of whether they declined therapy, or whether other protocol deviations are known.

Additionally, a comparison of the randomized treatment groups with regard to efficacy will be performed in the 'per-protocol set' (PP). This is a subset of the patients in the full analysis set and includes only patients for whom no major protocol violations are known. Comparisons of the treatments in the 'per protocol set' will be performed for the purpose of sensitivity analysis. Major protocol violations will be defined in the statistical analysis plan.

Safety analyses will be performed in the safety population (SAF). This is a subset of all randomized patients and includes patients who participated in at least one group session. Patients in the SAF will be analysed according to intervention received.

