### 2.3 Secondary endpoints

Risk of falling at 12 months will be defined as in 2.2 within 12 months.

Injurious falls (total number) are subdivided by “moderate” and “serious” [48]:

- 1) Moderate injurious falls are defined as those that resulted in sprains, bruises, scrapes, or joint injuries or if the individual needed medical care
- 2) Serious injurious falls are defined as those that resulted in a fracture, head injury, tendon rupture, or admission to a hospital (inpatient care), or that required stitches.

The BBS is a 14-item scale primarily assessing standing balance and sit-to-stand positions. Scores are based on a 5-point scale, rating from 0 to 4, based on performance quality and duration, or assistance needed. “0” indicates the lowest and “4” the highest level of function. The total score ranges from 0 to 56 points [50].

The MoCA is a brief cognitive screening tool for mild cognitive impairment and assesses several cognitive domains. The total sum score ranges from 0 to 30 and higher scores indicate higher functioning [51].

The Short FES-I is a 7-item questionnaire to measure fear of falling in elderly patients during different activities. It is to be filled out by the patient him/herself. Each item is rated on a four-point scale from 1 (not at all concerned) to 4 (very concerned). The total score ranges from 7 (no concern about falling) to 28 (severe concern about falling) [49].

The GDS-15 is a short, 15-item instrument, developed and validated for measurement of depressive symptoms among elderly people. It is to be filled out by the patient him/herself. Its items require a yes/no response. The total score ranges from 0 to 15. Sum scores 0-4 are considered normal, sum scores 12-15 indicate severe depression, in between as mildly depressed [52].

The SF-12 is a short-form generic measure of health status from the patient’s point of view. It is to be filled out by the patient him/herself. It contains 12 items on 8 health concepts. Results are expressed in terms of two meta-scores: Physical Component Summary and Mental Component Summary. Scores range from 0 to 100. Higher scores indicate better functioning. The mean score in a representative sample of the US population is 50 [53].

The IADL evaluates complex instrumental activities of daily living, on 8 items. The total score ranges from 0 to 8 in women, and from 0 to 5 in men [54].

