## 10 Safety monitoring and reporting

### 10.1 Complications

#### 10.1.1 Definition of complications

Only complications that could arise from the study specific intervention (EYT or Tai Chi or other exercises in the standard care group) will be collected, documented and – in case of serious complications – reported to the Data Monitoring Committee, DMC (details see chapter 10.3 and DMC Charter). A complication in the ENTAiER study is defined as any untoward medical occurrence in a trial patient such as any unfavourable and unintended sign, symptom, or disease that is possibly related to the study intervention. As the (non-pharmacological) intervention (EYT and Tai Chi) is training of musculoskeletal, sensory, concentrative elements, complications can be:

- Injuries caused by falls that happened during exercises in groups or at home.
- Musculoskeletal pain – except aching muscle - (e.g. foot, knee, low back pain, arthritis, joint effusion, reduced joint function), neuralgia, cardiovascular disorders (e.g. dizziness or faintness, symptoms of hypotension or hypertension, syncope, chest pain, cardiac arrhythmia), vertigo, dizziness, fatigue, syncope, dyspnoea, bronchospasm, dyspnoea, neurological cognitive disturbance, confusion, mood alteration, or others.

Not regarded as complications are

- conditions that were already present at the time of informed consent  
aching muscle ('Muskelkater'), which is to be expected.

The expression "related" means, that there is evidence or argument to suggest a reasonable causal relationship between the event and the administration of the intervention, e.g. close temporal connection, exclusion of other causes.

The assessment "not related" is appropriate, if the complication is clearly or most likely explained by other causes even if a potential relationship between treatment and the complication cannot be completely excluded.

Falls and injurious falls will be documented as primary outcomes. In case they happen during exercises in groups or at home, this will be noted. They will also be reported to the study center by therapists or teachers in case that they happen during exercises. Injuries caused by falls that happened during exercises in groups or at home will be documented as complications and indicated as caused by a fall. All falls that happen during exercises in groups or at home will be reported to the DMC with the regular report on complications.

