### 10.1.2 Documentation of complications

All such complications as defined in 10.1.1 reported by the patient or observed by the investigator, teacher or therapists will be continuously documented in the designated case report form (Complications form) during the clinical trial/at each follow-up visit.

Patients will be asked using open questions regarding their condition and any untoward medical occurrences during the last four weeks or any unplanned visits to a doctor, ambulance or hospital. In case of an occurrence, causal relationship with the study intervention EYT or Tai Chi, or, for instance in case of patients allocated to standard care alone, with physical training will be assessed.

In case of a potential causal relation to the intervention, the complication has to be documented in the CRF starting from the first administration and until at least 7 days after the last administration of the intervention.

Following information will be documented:

- Characterization of the event
- Onset date, if available
- Severity: see “assessment of severity” (see Section 10.1.3))
- Serious or non-serious
- Action taken with Intervention
- Outcome

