## 10.2 Serious Complications

### **10.2.1 Definition and documentation of serious complications**

In compliance with ICH-GCP (guideline E6 [R2]) section 4.11 and 5.17 we have taken the decision that the documentation and expedited reporting should be limited to events showing a causal relationship to the study procedure. For this reason, the investigator is obliged to document only the following events:

- Death of the patient,
- Life-threatening situation (patient is at immediate risk of death),
- Persistent or significant disability/incapacity.

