#### 14.5.2 Secondary endpoints

For the analysis of the secondary endpoint total number of falls per patient within 6 months after handing out the study book, a negative binomial regression model will be used to test the efficacy of EYT versus Tai Chi versus standard care. Negative binomial is preferred over Poisson regression because of potential overdispersion. Fall rates for patients with follow-up times of less than 6 months will be adjusted by accounting for their exposure time. The model will include intervention type, study site, BBS score, and age as independent variables. Incidence rate ratios (IRR) between interventions will be calculated from the model with two-sided 95% CI. To take into account potentially present excess zeroes, a zero-inflated negative binomial model will be used as a sensitivity analysis

Other secondary endpoints will be analysed with appropriate regression models. Analyses will be repeated for the observation period of 12 months after date of handing out the study book. This also applies to the primary endpoint at 12 months.

As a sensitivity analysis these analyses above will be repeated in the PP.

Safety analyses will be performed in the SAF. Rates of complications will be calculated with two-sided 95% CI.

No formal interim analyses of the efficacy endpoints will be performed.

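### The safety population admits only patients who attended a group session, so no complication rate can be calculated for standard care

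*Protocol*

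**What the plan says.** Three statements in the Protocol fix the safety analysis.

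- Section 14.4, on who belongs to the SAF: "This is a subset of all randomized patients and includes patients who participated in at least one group session".
- Section 14.4, on how they are grouped: "Patients in the SAF will be analysed according to intervention received".
- Section 14.5.2, on what is done: "Safety analyses will be performed in the SAF", followed by "Rates of complications will be calculated with two-sided 95% CI".

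Elsewhere the Protocol treats safety as a question for all three arms. The secondary objectives in the Synopsis and in section 3.1 compare EYT, Tai Chi and standard care alone on safety, among other outcomes, out to 12 months. Section 10.1.1 includes in the complications to be collected those arising from the study-specific intervention, which it spells out as "EYT or Tai Chi or other exercises in the standard care group". Section 10.1.2 has the causal relation to physical training assessed in patients allocated to standard care. The flowchart in section 6.1 schedules complications at every visit from month 1 to month 12, with no restriction by arm.

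**The concern.** Section 8 gives group sessions to EYT and Tai Chi patients only. Standard care has none, and section 8.2 says that neither EYT nor Tai Chi should be used in that arm. A rule that makes attendance at a session the condition of entry therefore shuts out the whole control arm by construction. Low adherence plays no part in it.

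At stake is the control-arm complication rate. Safety stands in the trial title beside efficacy, with standard care alone as the comparison, and section 2.1 asks whether the two exercise programmes cause harm. Complications would be recorded in the standard-care arm every month and then fall outside the only set in which they are to be analysed.

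**Working it through.** The Protocol states no size for the SAF, so there is no figure of its own to reproduce on this point. Its only sizing figure, 155 per group for the three-group chi-square test (section 14.3), reproduces: with faller proportions 0.50, 0.35 and 0.35 and alpha 0.05 on 2 degrees of freedom, 155 is the smallest group size with at least 80% power (power 0.802). That figure does not depend on the SAF.

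The check itself is a count of who can satisfy the membership rule.

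**Inputs**
- Randomised: 550 (section 3.4), allocated 1:1:1 (section 3.2).
- Group sessions: EYT and Tai Chi only (sections 8 and 8.1).
- Standard care: brochure and advice to see the primary care physician (section 8.1).

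**Largest possible SAF as written**
- Per arm: 550/3 = 183.3, about 183.
- EYT: up to about 183. Tai Chi: up to about 183. Standard care, analysed as standard care: 0.
- Total: at most 2 × 550/3 = 366.7, about 367 of 550. One third is excluded by definition.

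**Contamination does not help.** A standard-care patient who attends an EYT or Tai Chi session does meet the rule, but grouping by intervention received then counts that patient under EYT or Tai Chi. The standard-care column stays empty either way.

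**With the session requirement confined to the two exercise arms**
- Up to about 183 standard-care patients are added. The SAF could reach 550 if every EYT and Tai Chi patient attends at least once.

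**What the missing rate would offer.** The Protocol gives no expected number of control complications, so two assumed counts serve as illustration, with exact (Clopper-Pearson) intervals for n = 183:

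| Assumed complications | Rate | 95% CI |
|---|---|---|
| 0 | 0% | 0% to 2.0% |
| 6 | 6/183 = 3.3% | 1.2% to 7.0% |

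As written, neither line could be calculated.

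**Documentation window.** Section 10.1.2 has complications documented "starting from the first administration and until at least 7 days after the last administration of the intervention", and section 10.2.2 uses a similar window for serious complications. Neither names an equivalent for standard care. The flowchart supplies a start, since its Day 0 row covers the start of treatment or control, and section 5.2 starts observation at study-book hand-out in all arms. The end is not settled: section 3.3 puts no time limit on standard care, so there is no last administration to count from.

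**The case against.** The strongest defence has three parts.

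First, a complication here is by definition possibly related to the intervention and is not an all-cause adverse event. Restricting the denominator to exposed patients is then understandable, and a rate tied to exercise that controls choose for themselves is a different quantity. This stands as a caution on interpretation. It does not remove the conflict with sections 10.1.1 and 10.1.2, which have that quantity collected and assessed.

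Second, the data are gathered regardless, and section 14 lets the statistical analysis plan change an analysis if the change is marked and justified. So nothing is irretrievably lost. But for the analysis sets, section 14.4 defers only the definition of major protocol violations to that plan. The SAF itself is fixed in the Protocol, and fixed wrongly.

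Third, much harm information lies outside the SAF. Falls and injurious falls are endpoints in all three arms; hospital stays and physician contacts come from the FIMA, which section 10.1.1 names as further safety information; and death without a previous fall is a competing event with displayed cumulative incidence (section 14.5.1). This is correct and limits the damage.

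Three stronger readings are tempting and are not supported.
- A reader might infer that no safety comparison is possible. EYT versus Tai Chi remains available, and the planned analysis is descriptive, so a rate is lost and not a formal test.
- A reader might infer that the documentation window has no start for controls. The flowchart and section 5.2 provide one.
- A reader might infer that section 10.2.1, where "the investigator is obliged to document only the following events" introduces a list without hospital admission, contradicts section 2.3, where a fall leading to admission is a serious injurious fall. These are two constructs: a grading of injurious falls, and an explicit, reasoned limit on which complications are documented as serious. A fall with admission is still recorded under section 2.3, and all falls during exercises are reported to the Data Monitoring Committee.

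**Conclusion.** Wrong as written. Under sections 14.4 and 14.5.2 the standard-care arm contributes 0 of about 183 patients to the safety analysis, and its complication rate with 95% CI cannot be calculated. This contradicts the three-arm safety objective in the Synopsis and section 3.1, and the collection and assessment of complications in standard care in sections 10.1.1 and 10.1.2.

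The defect is confined to the control-arm complication rate and the descriptive contrast of each exercise arm with it. The sample size, the primary analysis and the endpoints analysed outside the SAF are untouched.

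The conclusion assumes that the membership rule in 14.4 is exhaustive, as the parallel definitions of the other two sets in that section suggest, and that a group session means an EYT or Tai Chi session, the only kind the Protocol describes. The count of 183 assumes that the full 550 are randomised in equal thirds; the zero does not depend on it.

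**What to change.** 1. **Section 14.4.** Apply the group-session requirement only to patients allocated to EYT or Tai Chi. Let standard-care patients enter the SAF from study-book hand-out (Day 0), analysed as standard care unless they attended an EYT or Tai Chi session.
2. **Exercise-arm patients with no session.** Do not count them as standard care. Their study book contains manuals, a DVD and a video link for home practice (section 5.2), and injuries from falls during home exercise are complications (section 10.1.1). Reassigning these patients would charge complications of EYT or Tai Chi practice to the control arm.
3. **Sections 10.1.2 and 10.2.2.** State that documentation for standard-care patients starts at Day 0. Reconcile the end of the window with the flowchart and section 6.4, which collect complications at every visit to month 12. A window closing at month 6 would fall short of the 12-month safety objective.

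The cost is a short rewording of 14.4 and a sentence in each of the two documentation sections. No visits or data items are added, because section 6.4 already has all patients interviewed monthly about complications. If the Protocol is not amended, the same change can be made in the statistical analysis plan before the treatment allocation is examined, marked and justified as section 14 requires.
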